### 7.2.2 Exclusion Criteria

1. Patient with past medical history or ongoing presence of other types of liver disease including, but not limited to, the following:
  - a) Biliary atresia of any kind
  - b) PFIC
  - c) Benign recurrent intrahepatic cholestasis
  - d) Suspected or proven liver cancer or metastasis to the liver on imaging studies

2. Patient with a past medical history or ongoing presence of any other disease or condition known to interfere with the absorption, distribution, metabolism (specifically bile acid metabolism), or excretion of drugs in the intestine, including but not limited to, inflammatory bowel disease
3. Patient with past medical history or ongoing chronic (i.e. >3 months) diarrhea requiring intravenous fluid or nutritional intervention for treatment of the diarrhea and/or its sequelae
4. Patient has a confirmed past diagnosis of infection with human immunodeficiency virus or other present and active, clinically significant chronic infection
5. Recent infection requiring hospitalization or treatment with parenteral anti-infective within 4 weeks of randomization (Study Day 1) or completion of oral anti-infective treatment within 2 weeks prior to start of Screening Period
6. Cancer within the last 5 years except for basal cell carcinoma
7. Cancer >5 years prior to screening except for non-liver cancers with no evidence of recurrence
8. Chronic kidney disease with an impaired renal function and a glomerular filtration rate <70 mL/min/1.73 m^2
9. Patient with surgical history of disruption of the enterohepatic circulation (biliary diversion surgery) within 6 months prior to start of Screening Period
10. Patient has had a liver transplant or a liver transplant is planned within 6 months of randomization
11. Decompensated liver disease, history or presence of clinically significant ascites, variceal hemorrhage, and/or encephalopathy
12. INR >1.4 (the patient may be treated with Vitamin K intravenously, and if INR is ≤1.4 at resampling the patient may be randomized)
13. Serum ALT >10 × ULN at Screening
14. Serum ALT >15 × ULN at any time point during the last 6 months unless an alternate etiology was confirmed for the elevation
15. Total bilirubin >15 × ULN at Screening
16. Patient suffers from uncontrolled, recalcitrant pruritic condition other than ALGS. Examples include, but not limited to, refractory atopic dermatitis or other primary pruritic skin diseases

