#### **10.1.3 Recording of Adverse Events**

Patients must be carefully monitored for the development of any AEs during the safety reporting period.

All observed AEs and any AEs that are spontaneously reported by the patient/caregiver will be recorded by the investigator. For all AEs, the severity, seriousness, and causality to study drug for each AE as outlined in [Section 10.1.2](#) will be assessed and recorded in the eCRF.

Any AE assessed as serious must be reported within 24 hours of site awareness.

Any SAEs or AEs that lead to permanent discontinuation of study drug that are unresolved at the time of the last study visit will be followed up by the investigator until resolution or stabilization. Following the last study visit, the Sponsor will provide forms for reporting additional information for any patient with ongoing SAEs or AEs that led to permanent discontinuation of study drug. Albireo retains the right to request additional information for any patient with ongoing AE(s) or SAE(s) at the end of the study.

Treatment-emergent AEs are defined as any AE that occurs after first dose of study drug. All SAEs that occur in the Screening Period, i.e. after enrollment and prior to first dose of study drug, will be collected as non-treatment emergent SAEs.

If there is a clinically significant deterioration of a laboratory value/vital sign or other routine study assessment that is associated with a diagnosis, the clinical diagnosis will be reported

as an AE and the associated signs and symptoms will be considered additional information unless the sign or symptom is more severe than expected given the diagnosis. For example, in a patient diagnosed with hepatitis during the safety reporting period, hepatitis would be considered the AE. Signs and symptoms of abdominal pain, vomiting, and elevated ALT and AST would not be reported separately unless, in the opinion of the investigator, one of these signs or symptoms is more severe than expected and therefore a separate AE assessment is indicated.

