### **10.2 Laboratory Values/Vital Signs/Physical Examinations and Other Safety Assessments**

#### **10.2.1 Laboratory Assessments**

Samples will be collected for clinical chemistry, hematology, and urinalysis testing at the time points specified in [Table 1](#). The parameters assessed are presented in [Table 4](#).

At screening, alkaline phosphatase will be fractionated (liver, bone, and intestinal isoenzymes) for patients  $\geq$  age 18 at the time of enrollment. If alkaline phosphatase is elevated during the treatment period, isoenzymes can be re-measured to assist in evaluation of the alkaline phosphatase elevation.

Blood for AFP measurement will be drawn at randomization (Study Day 1) and Week 24/EOT visits. Blood for measurement of fat-soluble vitamin levels including vitamins A and E, and 25-hydroxy vitamin D will be drawn at Screening Visit 1, randomization (Study Day 1), Week 12, and Week 24/EOT visits. Blood for INR (surrogate for vitamin K) will be drawn at Screening Visit 1, randomization (Study Day 1), Week 4 to 24/EOT, and Safety Follow-up visits. Patients will fast (water intake only is permissible) for at least 4 hours prior to the collection of samples for vitamin A. Exceptions can be made for infants, <12 months of age, if unable to fast for the full 4 hours. If a patient has any vitamin level(s)

that are outside of the reference range, vitamin supplementation adjustments may be required. Target ranges and supplementation strategy guidelines can be found in [Appendix 5](#).

A serum pregnancy test will be performed at Screening Visit 1. A urine pregnancy test will be collected at all other visits for females who have reached menarche. If a urine pregnancy test is positive, a serum pregnancy test is to be performed to confirm the pregnancy. Study drug administration will be held pending the confirmatory results. If the serum pregnancy test is negative, the patient can resume dosing. If the serum pregnancy test is positive, the patient is to be discontinued (see [Section 10.2.9](#)).

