#### **10.2.2.5 Fat-soluble Vitamin Deficiency (FSV)**

Patients with cholestatic liver disease are at risk for the development of FSV

deficiency. The investigator should assess patients for the following signs and symptoms of FSV deficiency at screening, at each study visit, and at the end of treatment visit per the Schedule of Assessments (Table 1):

- Vitamin A deficiency: night blindness, blindness, dry eyes, hair loss
- Vitamin D deficiency: osteopenia, fractures, muscle weakness, impaired wound healing
- Vitamin E deficiency: muscle weakness, difficulty walking, tremors, vision problems, poor immune function
- Vitamin K deficiency: bleeding difficulties

If, despite vitamin supplementation, levels of one or more of the fat-soluble vitamins remain low and in the Investigator's opinion presents a significant risk to the patient, treatment with study drug should be interrupted. If the fat-soluble vitamin levels improve and are no longer considered to pose a serious risk, study drug may be restarted at the Investigator's discretion. Fat-soluble vitamin levels should be monitored.

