4.8 Safety Analyses

Safety criteria are as follows:

- Primary safety analysis is the incidence of TEAEs and TEAEs categorized by causality, severity, and seriousness assessments made by the investigator by comparing active arms vs. placebo. This includes liver-related mortality and liver decompensation events (protocol Section 10.2.2.3) and all-cause mortality.
- Safety will also be evaluated by the following assessments:
 - Physical examinations
 - Concomitant medications
 - Vital signs
 - Laboratory test results (including clinical chemistry, hematology, urinalysis, AFP, vitamins A and E, 25-hydroxy vitamin D, and INR)
 - Abdominal ultrasound
 - Discontinuations due to AEs

All safety analyses will be performed on the SAF unless otherwise specified, using the following common rules:

- The analysis of the safety variables will be analyzed using descriptive statistics and summaries by treatment group for each cohort.
- No inferential statistical analysis will be planned.
- For each safety variable, the last value collected prior to first dose of study drug will be used as the baseline for all analyses.

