4.8.1 Adverse Events

General common rules for summarizing adverse events

All AEs will be classified by SOC and PT using the MedDRA version 25.0.

AEs will be classified as TEAEs, defined as follows: An AE (classified by preferred term) that occurs during the Treatment Period will be considered a TEAE if it has a start date on or after the first dose date of study drug, or it has a start date before the date of the first dose date of study drug but worsened in severity on or after the date of the first dose date of study drug.

AEs with missing start dates, but with stop dates either overlapping with the treatment period or missing, will be considered TEAEs. A TEAE with missing drug-relationship will be considered as related. A TEAE with missing severity will be considered as CTCAE grade 3 (severe). Details for imputing missing or partial start dates of adverse events are described in [Appendix 5](#). AEs with the same AE reference number that is collected on AE page of eCRF are counted as one AE only.

Adverse events of interest (AEIs)

Adverse events of interest (AEIs) will be selected for analyses as indicated in [Table 6 - Selections for AEIs](#).

Table 6 – Selections for AEIs

AEIs	Selection
Liver Decompensation	
a. The following TEAEs will be included:
 
PT = International normalised ratio increased and checkbox that event is refractory to vitamin supplementation is checked and at least 1 INR value (within 2 weeks [+/-] of the AE started date) is >1.5
 
PT = Vitamin K increased and checkbox that event is refractory to vitamin supplementation is checked and at least 1 INR value (within 2 weeks [+/-] of the AE started date and checkbox) is >1.5
 
PT = Hepatic failure, Acute on chronic liver failure, or Subacute hepatic failure
 
b. The following TEAEs occurring as separate events or in the presence of (i.e. ongoing medical history or AE) PT of portal hypertension and/or PT of hepatic cirrhosis were included:
 
PT = Ascites
 
PT = Hepatorenal syndrome
 
PT = Portopulmonary hypertension
 
PT = Oesophageal varices haemorrhage
 
PT = Gastric varices haemorrhage
 
PT = Intestinal varices haemorrhage
 
PT = Hepatic encephalopathy

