Liver Related	
The following Standardised MedDRA Queries (SMQs) will be included:
 
 • Drug related hepatic disorders – comprehensive search SMQ (narrow and broad) • Biliary tract disorders SMQ • Gallbladder related disorders SMQ • Gallstone related disorders SMQ
FSV Deficiency refractory to clinically recommended vitamin supplementation based on CRF	Both questions of “Is this an event of fat-soluble vitamin deficiency?” and “Is this refractory to clinically recommended vitamin supplementation?” on the AE page are checked as “Yes”.
Possible Sequelae of FSV Deficiency	Specified TEAEs with PTs are listed in Appendix 10

AEIs	Selection
Clinically Significant Diarrhea	
Clinically significant diarrhea is defined as diarrhea that persists for 3 or more days without any other etiology (e.g., infection) as assessed by the investigator, diarrhea reported by the investigator as severe in intensity or reported as an SAE or diarrhea with concurrent dehydration requiring treatment with oral or intravenous rehydration and/or other treatment intervention. Therefore, at least one of the following conditions met will be considered as clinically significant diarrhea:
 
 • PT = Diarrhoea or Diarrhoea haemorrhagic, and last for ≥ 3 days and the CRF question of “Does this event have a clear etiology (e.g., Infection)?” on the AE page is checked as “No”. • PT = Diarrhoea or Diarrhoea haemorrhagic and CTCAE ≥ 3 • PT = Diarrhoea or Diarrhoea haemorrhagic and SAE = “Yes” • PT = Diarrhoea or Diarrhoea haemorrhagic and the CRF question of “Is this an event of diarrhea with concurrent dehydration requiring treatment with oral or intravenous rehydration and/or other treatment intervention?” on the AE page is checked as “Yes”

Analysis of all adverse events

An overall summary of the incidence of TEAEs (number of patients with any events and number of events, if applicable) will include the following:

- Overview of the incidence of TEAEs
- Drug-related TEAEs (AE will be defined as drug-related if causality is either probable, possibly, or definitely related)
- TEAEs by CTCAE grades 1, 2, 3, 4, 5
- TEAEs leading to study drug discontinuation
- TEAEs leading to study drug interruption
- TEAEs leading to study drug dose reduction
- Serious TEAEs
- Drug-related serious TEAEs
- TEAEs leading to death
- Any hepatic TEAE

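### SAP Table 6 selects liver decompensation on a vitamin K term that points the wrong way, so a refractory low vitamin K event can be missed

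*SAP*

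**What the plan says.** SAP 4.8.1, Table 6, defines the adverse events of interest by preferred term (PT). Liver Decompensation part a has three rows:

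- Row 1: PT *International normalised ratio increased*, with the refractory checkbox ticked and at least one INR above 1.5 within two weeks either side of the event start.
- Row 2: "PT = Vitamin K increased and checkbox that event is refractory to vitamin supplementation is checked and at least 1 INR value", again above 1.5 in the same window. Here the window bracket carries extra words, "of the AE started date and checkbox", which row 1 does not have.
- Row 3: three hepatic failure terms, with no further condition.

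Part b lists seven complications, from ascites to hepatic encephalopathy.

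SAP 4.8 makes this category part of the primary safety analysis: "This includes liver-related mortality and liver decompensation events". The Table 6 definition then drives the TEAE overview, the SOC/PT tables, the exposure-adjusted incidence rates and the optional Kaplan-Meier displays in SAP 4.8.1.

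**The concern.** The three conditions in row 2 do not describe one clinical picture. A patient whose INR stays high although vitamins were given is short of vitamin K or cannot use it. A finding of too much vitamin K would not be called refractory to supplementation. The row therefore selects essentially no events.

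Row 2 sits beside row 1 with the same checkbox and INR conditions. This suggests that it was meant to catch the same episode when it is coded under the vitamin rather than under the laboratory sign. If so, that second route is closed, and a liver safety event could be misclassified in a trial with few patients per arm. A correction made after unblinding would also be a post hoc change to a safety definition.

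**Working it through.** The plan gives no figure for this point, so the check is on direction first, then on the selection logic, then on scale.

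**1. Which way vitamin K should point**

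- Protocol 10.2.1: "Blood for INR (surrogate for vitamin K) will be drawn". INR stands in for vitamin K status.
- Protocol 7.2.2, exclusion 12: when INR is too high at screening, "the patient may be treated with Vitamin K intravenously". A high INR is handled as a shortage.
- Protocol 10.2.2.5: the monitored problem is deficiency, and failed supplementation is described as "If, despite vitamin supplementation, levels of one or more of the fat-soluble vitamins remain low".
- Vitamin K itself is not in Protocol Table 1, Protocol Table 4 or the laboratory list in SAP 4.8.2.1. No scheduled result could give rise to an *increased* term.

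**2. Test events through the rows as written**

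Each event has the refractory box ticked and an illustrative INR of 1.8 inside the window. The documents do not give the low vitamin K labels, so those used here are assumed.

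| Coded term | Row matched, as written | Row matched, if row 2 named low terms |
|---|---|---|
| International normalised ratio increased | a, row 1 | a, row 1 |
| Vitamin K increased | a, row 2 | none |
| Vitamin K decreased (assumed label) | none | a, row 2 |
| Vitamin K deficiency (assumed label) | none | a, row 2 |

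**3. Can an event be coded only under the deficiency?**

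Protocol 10.1.3 says of a laboratory deterioration "that is associated with a diagnosis, the clinical diagnosis will be reported" as the AE. The associated signs are not reported separately unless they are worse than expected. The AE page also asks whether an event is a fat-soluble vitamin deficiency, and "Is this refractory to clinically recommended vitamin supplementation" (SAP Table 6). A single event coded as vitamin K deficiency, with no separate INR event, is therefore plausible.

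**4. Scale of one missed patient**

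This is illustration only. It assumes a 2:1 split and no other such event in the arm.

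- 45 randomized (SAP 2.1), 30/15: 1/30 = 3.3%; 1/15 = 6.7%.
- Largest size in SAP Table 4, 54 completers, with the planned 20% drop-out applied: 54/0.80 = 67.5, about 68, split 45/23: 1/45 = 2.2%; 1/23 = 4.3%.
- Exposure-adjusted rate at 30/15, with 168 days at risk for every patient without the event. The event falls on day 168 (lower figure) or day 1 (upper figure):
  - Odevixibat: 30 × 168 = 5040 days = 13.80 patient-years, 100/13.80 = 7.2; 29 × 168 + 1 = 4873 days = 13.34 patient-years, 100/13.34 = 7.5 per 100 patient-years.
  - Placebo: 15 × 168 = 2520 days = 6.90 patient-years, 100/6.90 = 14.5; 14 × 168 + 1 = 2353 days = 6.44 patient-years, 100/6.44 = 15.5 per 100 patient-years.
- SAP 4.8.1 counts time at risk to the last participation date. If every patient stayed to the Day 196 follow-up and the event came that day: 30 × 196/365.25 = 16.10 patient-years gives 6.2, and 15 × 196/365.25 = 8.05 patient-years gives 12.4.

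**The case against.** The strongest reply is that the gap is narrow. Vitamin K is not measured, so a laboratory-based *decreased* term is as unlikely as an *increased* one. The natural laboratory coding is a raised INR, which row 1 catches. The reporting rule in Protocol 10.1.3 does not say which diagnosis replaces the sign. It could be hepatic failure, which row 3 catches without any INR or checkbox condition. This stands as a limit: what remains is an event coded solely as a vitamin K deficiency diagnosis.

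Such an event would also not vanish. It stays in the general TEAE tables and the raised INR stays in the laboratory summaries. If both AE-page questions are answered yes, it also appears in the refractory fat-soluble vitamin category and its merged listing. The liver monitoring listing has an INR row of its own (threshold blacked out), and suspected drug-related hepatic injury goes to blinded adjudication (Protocol 11.2.4). Whether the Liver Related MedDRA queries would include it cannot be checked from the documents. All of this is fair, but none of these routes puts the event into the decompensation counts, rates or curves.

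Finally, SAP 4.8 points to Protocol 10.2.2.3 for decompensation. That section refers to Protocol Table 5, where the criteria are blacked out, so the intended wording of row 2 cannot be confirmed. This limits certainty about the exact replacement term. It does not remove the conflict inside row 2, which can be seen without Table 5.

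**Conclusion.** The concern holds. Row 2 names a term in the wrong direction and, followed literally, drops a refractory event with INR above 1.5 that is coded only as low or deficient vitamin K from every liver decompensation output. Nothing in either document corrects it.

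The number of events affected is unknown and may be zero. The per-patient figures show only how visible a single misclassification would be at this sample size. The rate figures move with the assumed time at risk.

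The safety analyses are descriptive, so alpha, power and the efficacy conclusions are untouched. The correction should be made, but the trial's main result does not depend on it.

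**What to change.** Before database lock, replace *Vitamin K increased* in Table 6, Liver Decompensation part a, row 2, with the low or deficient vitamin K preferred term(s). Verify the exact wording in MedDRA 25.0 and reconcile the row with the unredacted decompensation definition in Protocol Table 5. Leave the refractory-checkbox and INR conditions as the SAP has them. Delete the stray words in the INR-window bracket so that the row reads like row 1.

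The cost is one line in the SAP, the matching line in the selection program and one dictionary check. No new data are needed and no clinical rule changes.

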Summary tables for number of patients with any TEAEs by SOC and PT by severity (grade 1 to grade 5) and by causality (related [possibly, probably, and definitely] vs unrelated [unlikely and unrelated]), will also be provided. AEs with the worst severity will be used in the by-severity summaries. Similarly, AEs with the worst causality (most related to treatment) will be used in the by-causality summaries. If severity or causality is missing, data will be imputed as grade 3 or related, respectively.

When a patient has the same adverse event, based on preferred terminology, reported multiple times during the study, the patient will only be counted once at the preferred terminology level in adverse event frequency tables. Where a patient has multiple adverse events within the same SOC during the study, the patient will only be counted once at the SOC level in adverse event frequency tables. In the AE summaries, AEs will be sorted by alphabetically for SOC and PT.

In addition to the frequency summary of TEAE tables, the exposure adjusted incidence rate (EAIR) (per 100 patient years at risk) with the 95% confidence interval, based on Poisson distribution, will also be provided for each of the following AE tables:

- TEAEs by SOC and PT
- Liver-related TEAEs by SOC and PT
- Liver Decompensation TEAEs (as defined in [Table 6 - Selections for AEs, for TEAEs listed in b in the presence of \(i.e. ongoing medical history or AE\) PT of portal hypertension and/or PT of hepatic cirrhosis](#)) by SOC and PT
- FSV Deficiency refractory to clinically recommended vitamin supplementation TEAEs by SOC and PT
- Possible Sequelae of FSV Deficiency TEAEs by SOC and PT
- Clinically Significant Diarrhea TEAEs by SOC and PT

The EAIR (per 100 patient years at risk) will be calculated as follows:

$$\text{Number of subjects with event} / \text{Total cumulative time at risk (years)} \times 100$$

where total cumulative time at risk is the sum of individual time at risk. The time at risk for a subject with the event of interest will be calculated (in years) as:

$$(\text{first event date} - \text{date of first dose} + 1) / 365.25$$

The time at risk for a subject without the event of interest is calculated as:

$$(\text{last participation date} - \text{date of first dose} + 1) / 365.25$$

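### SAP Table 6 counts three hepatic failure terms as liver decompensation but not the acute form, so an acute failure coded to its own term could be left out of the decompensation outputs

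*SAP*

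**What the plan says.** SAP section 4.8.1 sets the coding level for all adverse events: "All AEs will be classified by SOC and PT using the MedDRA version 25.0". Table 6 (Selections for AEIs) then defines liver decompensation by named preferred terms (PTs).

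- **Part a, INR rows.** There are two laboratory-type rows. The first reads "PT = International normalised ratio increased and checkbox that event is refractory to vitamin supplementation is checked" and also needs an INR above 1.5 within two weeks of the event's start. The second sets similar conditions on a vitamin K term.
- **Part a, failure row.** "PT = Hepatic failure, Acute on chronic liver failure, or Subacute hepatic failure".
- **Part b.** Seven complications: ascites, hepatorenal syndrome, portopulmonary hypertension, three variceal haemorrhage terms and, last, "PT = Hepatic encephalopathy". None is a failure term.

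The separate Liver Related category is built differently, from standardised MedDRA queries. The first is "Drug related hepatic disorders – comprehensive search SMQ (narrow and broad").

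On use, SAP section 4.8 says of the primary safety analysis: "This includes liver-related mortality and liver decompensation events (protocol Section 10.2.2.3) and all-cause mortality". Section 4.8.1 puts decompensation in the overview table and the SOC/PT tables. It also lists it among the exposure-adjusted incidence rates, in an entry that opens "Liver Decompensation TEAEs (as defined in" and points to Table 6, and among the events for which Kaplan-Meier curves may be drawn.

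**The concern.** The failure row is a closed list of exact terms. Because it names the acute-on-chronic and subacute forms beside plain hepatic failure, the plan does not treat the general term as covering qualified forms. On that logic a qualified form that is not named is not selected, and the acute form is not named. No acute hepatic or acute liver failure term stands anywhere else in the readable text.

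At stake is a small count in a category the SAP singles out. The protocol monitors for drug-induced liver injury (section 10.2.2), sets up a hepatic adjudication committee (section 11.2.4) and foresees hepatic failure requiring transplantation (section 7.2.4). In a trial of this size a decompensation table is likely to hold very few events, so one case decides whether an arm shows none or one.

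**Working it through.** The plan states no figure on this point, so the check is of the text, followed by simple scaling.

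**1. Is the acute form reached by the failure row?** The row has three PTs and selection is at PT level. An event coded to a separate acute hepatic failure PT matches none of them. That such a PT exists in MedDRA 25.0 is an assumption: the dictionary is not reproduced. The SAP's use of separate PTs for two sibling forms makes it plausible but does not prove it.

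**2. Is the patient reached by another route?**

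| Route | What it needs | Reliability |
|---|---|---|
| Part a, INR row | Its own INR-increased event, the refractory box ticked, and an INR above 1.5 | Depends on the INR rise being recorded apart from the diagnosis |
| Part b | A separately recorded complication, such as hepatic encephalopathy | Same dependence; for the rate and the curve it also needs a portal hypertension or cirrhosis term |

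Protocol section 10.1.3 bears on both. Where a deterioration belongs to a diagnosis, the diagnosis is reported "as an AE and the associated signs and symptoms will be considered additional information unless the sign or symptom is more severe than expected". Its example is hepatitis, where raised ALT and AST are not reported separately unless worse than expected. A correctly reported acute failure may therefore generate neither an INR event nor a part b event.

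For the incidence rate and the Kaplan-Meier curve, section 4.8.1 counts part b terms only in the presence of portal hypertension or cirrhosis. A patient with acute failure, recorded encephalopathy and neither of those terms would be missing from both, although the encephalopathy would put the patient in one of the two overview versions and one of the two SOC/PT versions.

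**3. Where would the event still appear?** Under its own PT in the all-TEAE table and, as applicable, in the serious, grade 3 or higher, drug-related, discontinuation and death tables (SAP section 4.8.1). It would probably also fall under Liver Related, although the contents of the queries are not in the documents.

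**4. Scale of one uncounted case.** Inputs: 45 patients at 2:1 (SAP section 2.1), and treatment to day 168 (Protocol Table 1). Assumptions: arms split exactly 2:1, and every patient contributes 168 days at risk.

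- Arm sizes: 45 × 2/3 = 30 odevixibat; 45 × 1/3 = 15 placebo.
- Proportion: 1/30 = 3.3%; 1/15 = 6.7%.
- Patient-years: 30 × 168/365.25 = 13.8; 15 × 168/365.25 = 6.9.
- Rate for one event: 100/13.8 = 7.2 and 100/6.9 = 14.5 per 100 patient-years.

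Actual time at risk will differ, since it stops at a first event and otherwise runs to last participation. The rates are therefore approximate.

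**The case against.** **The separate term cannot be seen.** This stands. The point is conditional on a dictionary check. If MedDRA 25.0 has no such PT, nothing changes.

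**The list may be deliberate.** The SAP's version history says the Table 6 definitions were updated after regulator comments, and that correspondence is not available. An agreed omission cannot be ruled out. But the SAP gives no reason for it, whereas section 4.5.2 does give its reason for dropping changes in anti-pruritus medication as an intercurrent event.

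**These patients have chronic liver disease, so failure would be coded as acute-on-chronic or plain hepatic failure.** Possible, and both are listed. But the site supplies the diagnosis term (Protocol section 10.1.4), and nothing readable requires it to be recoded in the light of history.

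**The event is still reported.** This stands in full. A reader might infer that the case would surface only within the broad liver-related group. The SOC/PT tables show otherwise, and the adjudication committee and DSMB reviews (Protocol sections 11.2.3 and 11.2.4) are not tied to Table 6. Nor would every such case necessarily be missed: the INR and part b routes exist, even if they cannot be relied on.

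**The link to the primary safety analysis is loose.** Partly right. The primary safety analysis is the incidence of all TEAEs, which would include this event. For decompensation, SAP section 4.8 cites Protocol section 10.2.2.3, which refers to Protocol Table 5, whose criteria are redacted. Agreement between that definition and SAP Table 6 cannot be checked. Safety is descriptive, so no test or decision rule changes.

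**Conclusion.** The point holds as a limited gap in an event definition. If MedDRA 25.0 has a separate PT for acute hepatic failure, Table 6 part a does not select it, and the alternative routes depend on extra events that the protocol's recording rule tends to suppress. The outputs affected are the decompensation overview, SOC/PT tables and exposure-adjusted rate, together with the Kaplan-Meier curve if produced. One uncounted case is 3.3% of the odevixibat arm or 6.7% of placebo. No likelihood of such a case can be derived from the documents.

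Two wider readings are not supported. The event would not be lost from safety reporting, for the reasons given above. And a reader might infer that a chronic failure term has been wrongly omitted too; the documents give no argument for adding one.

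**What to change.** Before database lock, check the failure terms in Table 6 part a against MedDRA 25.0 and add acute hepatic failure to the row. If the sponsor left it out on purpose, state the reason beside the table. The cost is one line in the SAP and the matching line in the selection program. No new data are needed, and no other category changes.
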